3.1 Consent Process

Potential study participants will be approached by their medical oncologist at the time of their routine clinic visit during the aforementioned timeline. The physician will give the patient an Information Sheet that briefly outlines the study and answer any questions. Patients will be asked to provide oral consent to be randomized to one of the two pre-specified treatment arms. This integrated consent model is akin to a typical conversation between the physician and patient and the interaction is documented in the patient's

medical record. Written informed consent will not be sought as the integrated consent model is ethically acceptable as the only prominent change to the standard of care treatment is the randomization process and there is no evidence-based standard of care for dose timing of endocrine therapy.

4 *ELIGIBILITY*

4.1 Inclusion Criteria

- Patients with an early stage or locally advanced hormonal receptor positive breast cancer
- Plan to receive endocrine therapy
- Age ≥ 18 years
- Able to provide oral consent
- Willing and able to complete questionnaires as per study protocol

4.2 Exclusion Criteria

- Metastatic cancer
- Previous endocrine therapy for breast cancer
- Plan to receive adjuvant abemaciclib

5 *STATISTICAL ANALYSIS AND SAMPLE SIZE CALCULATION*

5.1 Sample size

Our primary outcome is the change in total FACT-ES score from baseline to 12 weeks following the beginning of endocrine therapy.

Based on Fallowfield et al., a clinically meaningful effect would be observed if the change exceeded 0.5 of the standard deviation at baseline and the standard deviation at baseline is approximately 8.5²⁵. Therefore a ‘clinically meaningful change’ from baseline to 12 weeks would be a change of 4.25 or greater. It is also assumed that 40% of patients will experience a clinically meaningful change, and prescribing the time of day for administration of treatment would be important if there was an actual difference in clinically meaningful change rates of 20% or more (i.e. 40% with a clinically meaningful change in one arm and 60% in the other). Therefore, based on these assumptions and using a two-sided, alpha=0.05 Fisher’s exact test, we would need 214 total patients to achieve 80% statistical power. To account for potential loss to follow-up, and to account for stratification factors, the target sample size will be inflated by 10% to a total of 235.

5.2 Analysis Methods

Descriptive analysis: Baseline characteristics will be presented with means (continuous measures) or proportions (categorical or ordinal data) with 95% confidence intervals.

Intention-to-treat analysis: The primary analysis will be based on the intent-to-treat principle, thus, all participants who are randomized will be included in the final study analysis. The last observation carried forward method will be used to impute results for any patient who is lost to follow-up, or who does not have a FACT-ES score measured at the 12 week time point. This is a conservative approach to imputation, as it will likely result in smaller differences between groups than would actually be present (if there is an actual difference), under the assumption that increased effects will occur over time up to week 12. In addition, a per protocol analysis of the primary outcome measure will be conducted,

which will include only those patients who follow the intervention as prescribed in the protocol, and who complete both the baseline and 12 week FACT-ES score.

Analysis of primary and secondary outcomes: Dichotomous outcomes will be summarized according to proportions and 95% confidence intervals. Continuous outcomes will be summarized according to means and standard deviations or medians and interquartile ranges as appropriate. The primary analysis will be based on a logistic regression analysis with adjustment for stratification factors. Additional logistic and linear regression analyses will be performed with adjustment for stratum. Univariable comparisons between the intervention and control groups will be examined using a Chi-Squared test for dichotomous events, and a student's t-test for continuous measures. Non-parametric methods may be used in lieu of these tests as appropriate. All analyses will be supplemented with 95% confidence intervals where relevant.

Health economic evaluation: We will perform a cost utility analysis alongside this pragmatic randomized controlled trial. Resource use and health utility values will be measured from the trial at the baseline and follow up interviews. We will derive health utility values from the European Quality of Life-5 Dimensions 5-level (EQ-5D-5L) questionnaire. We will develop a Markov model that represents lifetime experience of a patient cohort following her treatment option to predict the long-term prognosis of patients. The model will consist of multiple distinct states, representing breast cancer progression and relevant adverse events. It will also have the capacity to capture medication adherence. We will derive input parameters required for the model from the concurrent trial and the published literature. The results will be presented as incremental cost per quality-adjusted life year (QALY) gained and incremental cost per one endocrine toxicity

case averted. Both costs and outcome will be discounted at 1.5% annually. A series of sensitivity analysis will be undertaken to examine the effect of conducting a complete case only analysis and of varying input parameters. Parameter uncertainty will be assessed using Monte Carlo simulations with 10,000 simulations. The results of the simulations will be shown as effectiveness acceptability curves (CEACs), which represent the probability of a treatment being cost-effective to a range of potential threshold values that the health system may be willing to pay for an additional unit of effect. All analysis will be conducted using Microsoft Excel.

Compliance and loss to follow-up: Supportive analyses will be performed to better understand the impact of non-compliance, loss to follow-up and protocol violations. The primary analysis is clearly defined, and other analyses will be performed understanding the supportive and secondary nature of these results. Interpretation of results will be performed, clearly acknowledging the a priori defined primary analysis.

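### LOCF for the week-12 FACT-ES is called conservative, but it counts every baseline-only patient as a non-event; loss that differs by arm can create a difference, or enlarge one if the lower-rate arm loses enough more

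*Combined protocol and SAP*

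**What the plan says.** Section 5.2 sets the primary population by intention to treat: "all participants who are randomized will be included in the final study analysis". For missing data, "The last observation carried forward method will be used to impute results for any patient who is lost to follow-up", and likewise for anyone without a 12-week FACT-ES score. No minimum number of post-baseline scores is required. Section 3 schedules the questionnaire at baseline and weeks 4, 8, 12 and 52, so the value carried forward to week 12 can be the baseline score itself.

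The plan justifies the choice: "This is a conservative approach to imputation, as it will likely result in smaller differences between groups than would actually be present". That sentence is limited to the case where a real difference exists, and holds "under the assumption that increased effects will occur over time up to week 12".

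The primary model is a logistic regression adjusted for the stratification factors. Section 5.1 defines the event: a clinically meaningful change "from baseline to 12 weeks would be a change of 4.25 or greater". It is powered for "40% with a clinically meaningful change in one arm and 60% in the other". Sections 2.1 and 5.1 also word the primary outcome as the change in total score. This point rests on the binary reading, which the sample size and the logistic model support.

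Other analyses bear on missing scores. A per-protocol analysis covers patients "who follow the intervention as prescribed in the protocol, and who complete both the baseline and 12 week FACT-ES score". Section 5.2 also promises supportive analyses of non-compliance and loss to follow-up, without naming a method. The complete-case analysis mentioned there belongs to the health economic evaluation.

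**The concern.** A patient with no post-baseline score has an imputed change of exactly 0. That is below 4.25 whichever direction counts as worsening, so the patient is a non-event by construction. Each arm's analysed event rate then depends partly on how many of its patients never returned a post-baseline form.

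The plan's argument concerns growth of the effect over time. It does not address whether the two arms lose patients at the same rate. The trial is open-label (section 5.4), and section 9 lists toxicity and non-compliance among the reasons for withdrawal, so unequal or outcome-related loss is possible. If it occurs, the primary comparison can be biased in either direction, while the word conservative invites readers to treat a positive result as safe.

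**Working it through.** **Inputs.** Event rates 40% v 60%, threshold 4.25, two-sided alpha 0.05, 80% power, 214 patients inflated to 235 (section 5.1); 1:1 allocation (section 5.3); LOCF and logistic regression (section 5.2). Loss by arm is not given. The only related figure is that "the target sample size will be inflated by 10% to a total of 235", an allowance shared with stratification. The loss shares below are therefore assumptions.

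**The plan's own figure.** The uncorrected two-proportion formula gives (1.960 × √0.50 + 0.842 × √0.48)² / 0.20² ≈ 96.9, so 97 per arm. With continuity correction it is 107 per arm, 214 in total, as stated. Enumerated Fisher power at 107 per arm is 79.5%. 214 × 1.10 = 235.4, stated as 235.

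**Effect of LOCF on the rates.** Let d be an arm's share of baseline-only patients, and suppose loss is random within arm. The analysed rate is p × (1 − d). For a true 40% v 60%, the analysed difference is

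0.6(1 − d60) − 0.4(1 − d40) = 0.20 + 0.4·d40 − 0.6·d60.

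It exceeds 0.20 only if 0.4·d40 > 0.6·d60, that is d40/d60 > 1.5, with the heavier loss in the 40% arm. On the odds-ratio scale of the logistic model the threshold is slightly lower: 1.46 at d60 = 5% and 1.43 at d60 = 10%.

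**Rejection rates.** These come from exact binomial enumeration, 117 v 118 patients, with an uncorrected chi-square test standing in for the logistic model.

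No true difference, baseline-only loss by arm:

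| Loss | Type I error, event rate 40% | Type I error, event rate 60% |
|---|---|---|
| 10% v 10% | 5.0% | 5.0% |
| 8% v 12% | 5.7% | 6.5% |
| 5% v 10% | 6.1% | 7.3% |
| 5% v 15% (extreme) | 9.7% | 15.0% |

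True 40% v 60%, baseline-only loss as 40% arm / 60% arm:

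| Loss | Analysed rates | Difference (points) | Odds ratio | Power |
|---|---|---|---|---|
| none | 40% v 60% | 20.0 | 2.25 | 0.87 |
| 10/10 | 36.0% v 54.0% | 18.0 | 2.09 | 0.79 |
| 8/12 | 36.8% v 52.8% | 16.0 | 1.92 | 0.69 |
| 5/15 | 38.0% v 51.0% | 13.0 | 1.70 | 0.51 |
| 12/8 | 35.2% v 55.2% | 20.0 | 2.27 | 0.87 |
| 15/5 | 34.0% v 57.0% | 23.0 | 2.57 | 0.95 |

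Observed scores alone at 10/10 (105 v 106 patients) give power 0.84.

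**Patients lost later.** Those with a week 4 or 8 score carry that score and can be events. Under an assumed trajectory (SD 8.5, correlation 0.6, mean change at weeks 4 and 8 equal to 50% and 80% of that at week 12), 5% v 15% random loss after week 4 only gives type I error of 4.9% and 5.5%. The same loss spread over baseline, week 4 and week 8 gives 5.6% and 6.9%.

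**Loss that depends on outcome.** In a simulation on the same trajectory (4,000 replicates, strata-adjusted logistic model, site not simulated), 10% of patients already 4.25 worse at week 4 leave in the 40% arm and 30% in the 60% arm. A true 40% v 60% becomes 41.4% v 62.9% under LOCF (21.5 points), 39.3% v 57.2% with observed scores (17.9 points, power 0.76), and 40.1% v 59.9% under multiple imputation (power 0.85). Here LOCF enlarges the difference although the heavier loss is in the 60% arm, so the 1.5 threshold does not carry over.

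**The case against.** The plan's sentence is hedged: it says likely, applies only if a difference exists, and states its assumption. With equal random baseline-only loss it is correct. It makes no claim about the null case. Both arms take the same kinds of drug and differ only in the hour of intake, so loss may well be similar, and a chance imbalance with equal underlying loss leaves type I error at 5%. Section 9 concerns withdrawal from study treatment. Questionnaires go by electronic link or on paper, so a patient who withdraws may still return scores. Withdrawal reasons are already to be shown in the CONSORT diagram. If loss is random within arm, observed scores already recover 40% v 60%, and imputation adds little.

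All of this stands, and it limits the size of the point. It does not supply a reason why loss should be equal by arm. Nor does it supply a fallback: the per-protocol analysis mixes missingness with compliance, and the supportive analyses have no stated method.

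Three stronger readings are tempting. A reader might infer that any imbalance beyond 1.5-fold enlarges the effect. It does not: 5/15 is a threefold imbalance and shrinks the difference to 13 points. A reader might infer that LOCF always costs power unless it enlarges the difference. Against observed scores that is false: at 14/10 the difference is 19.6 points, yet power is 0.86 against 0.83. A reader might also take 10% to 15% as the trial's type I error. Those figures need systematic 5% v 15% loss, all of it before week 4, and nothing in the documents points to that.

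**Conclusion.** The point holds in limited form and should be fixed. On the binary reading, LOCF with no minimum visit makes every baseline-only patient a non-event, and the stated reason for calling it conservative does not cover loss that differs by arm. Under moderate, systematically unequal baseline-only loss (8% v 12% or 5% v 10%), type I error is about 5.7% to 7.3%. Equal 10% loss lowers power from 0.84 with observed scores to 0.79. Heavier loss in the higher-rate arm costs much more.

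Enlargement of a true 40% v 60% under random baseline-only loss needs the 40% arm to lose more than 1.5 times the share lost in the 60% arm on the risk-difference scale, or about 1.4 to 1.5 times on the odds-ratio scale. This assumes that lost patients would have had their own arm's event rate; if loss depends on outcome, these thresholds do not apply. The documents do not show that loss will be unequal, so they do not support a conclusion that the primary result will be inflated. They support only that its direction of bias is not secured.

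**What to change.** In section 5.2, keep the endpoint and the stratification-adjusted logistic regression, and change the handling of missing week-12 scores:

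- **Primary handling:** multiple imputation of the week-12 score from arm, baseline, week 4 and week 8 scores and the stratification factors; then dichotomise at 4.25 and combine by Rubin's rules.
- **Sensitivity analyses:** a pre-specified delta-adjusted or tipping-point analysis, needed because baseline-only patients have no week 4 or 8 score to inform the imputation; an analysis of all observed week-12 scores, not restricted to compliers; and LOCF.
- **Reporting:** missing week-12 scores by arm and last completed visit.
- **Wording:** delete the sentence calling LOCF conservative, or limit it to loss that is random and equal by arm.

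The cost is SAP text and a little programming, with no new data, visits or patients. The downside is reliance on a missing-at-random assumption, which the tipping-point analysis tests. Imputation's advantage over observed scores appears mainly when loss depends on the week 4 or 8 scores.

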2.2 Secondary Outcomes

- Endocrine toxicity and tolerability measured by the change in total score and individual items of FACT-ES from baseline to 4, 8, 12 and 52 weeks following the beginning of endocrine therapy
- Quality of life measured by the change in the total score and individual subscales of the validated Functional Assessment of Cancer Therapy for patients with a Breast cancer (FACT-B) questionnaire from baseline to 4, 8, 12 and 52 weeks following the beginning of endocrine therapy
- Rates of discontinuation, interruption and non-compliance (defined as patient taking less than 80% of the prescribed endocrine therapy) with initially prescribed endocrine therapy
- Cost-effectiveness: incremental cost-effectiveness ratios (cost per one quality-adjusted life year (QALY) gained

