3 STUDY DESIGN

The study schema is shown in Figure 1. Eligible patients with hormone receptor positive breast cancer who will receive adjuvant endocrine therapy will be eligible for this study. Patients will be consented either by their treating medical oncologist or a member of their circle of care. Consenting patients will be randomized to one of two arms:

Arm A: Morning administration of endocrine therapy defined as, within one hour of the patient wake up time.

or

Arm B: Evening administration of endocrine therapy defined as, within one hour of the patient bed time.

There will be no study mandated change in either the type of endocrine therapy. Endocrine therapy can be started either before, prior or after radiation therapy prescribed, as per patients' choice.

Patients will be approached by their medical oncologists during routine clinic visits. In order to ensure trial findings are applicable to the broadest population possible, eligibility

criteria will be pragmatic. Patients will be assessed either as per their usual clinic visits, or as the study does not involve additional clinic visits, study questionnaires will be completed via electronic link sent via email. The questionnaires will be built into the electronic database developed by the Ottawa Methods Centre and patients will receive a secure electronic link to complete the questionnaires at the required study timepoints. If patients do not have access to a computer/internet, they can request to receive paper copies in the clinic or by mail.

Outcomes will be measured at:

- Baseline (prior to start endocrine therapy)
- 4 weeks (\pm 1 week) after the start of endocrine therapy
- 8 weeks (\pm 1 week) after the start of endocrine therapy
- 12 weeks (\pm 2 week) after the start of endocrine therapy
- 52 weeks (\pm 2 week) after the start of endocrine therapy

The study calendar is shown in Table 1.

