5.3 Randomization and Stratification

Eligible and consented patients will be randomized using a permuted block design developed by the Ottawa Methods Centre to receive either one of the two study arms (1:1). The variable block sizes will be randomly selected between sizes of 4 and 6. Subjects will be stratified based on: study site, tamoxifen (yes/no), and chemotherapy (yes/no). The patient will be randomized through a secure web-based randomization system on the physician's clinic desktop or mobile device or through the designated study CRA. The randomization system also confirms the study eligibility criteria prior to randomization. The study does not involve changing the standard of care patients receive.

The study co-investigators (i.e. study qualified physicians) will ensure verbal consent and eligibility review has taken place prior to randomization. For all patients, the primary oncologist will dictate in the patient's electronic medical record that the consent process has taken place.

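### The FACT-ES and FACT-B models leave out the baseline score, which is already collected and would add precision and protect against chance imbalance

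*Combined protocol and SAP*

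**What the plan says.** Section 5.1 defines the outcome: "Our primary outcome is the change in total FACT-ES score from baseline to 12 weeks following the beginning of endocrine therapy". It then dichotomises it, since a clinically meaningful change "from baseline to 12 weeks would be a change of 4.25 or greater". Section 5.2 gives the model: "The primary analysis will be based on a logistic regression analysis with adjustment for stratification factors". For the rest it says: "Additional logistic and linear regression analyses will be performed with adjustment for stratum". Section 5.3 lists the stratification factors as study site, tamoxifen and chemotherapy. The univariable comparisons in 5.2 are chi-squared and t-tests.

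The secondary outcomes in 2.2 include "the change in total score and individual items of FACT-ES from baseline to 4, 8, 12 and 52 weeks", with FACT-B change at the same times. Section 3 and Table 1 schedule both questionnaires before endocrine therapy starts. No section names a baseline FACT score as a covariate, and randomisation does not balance it. The factors in 2.3 (age, stage, chemotherapy, type of therapy) concern persistence and compliance, not the FACT scores.

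**The concern.** It can look as if a change score has already adjusted for baseline. It has, but with the slope fixed at 1. If the slope of the 12-week score on the baseline score is below 1, as is usual, patients with high baselines tend to fall and those with low baselines tend to rise. Change is then still correlated with baseline, and so is crossing the 4.25-point threshold.

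Two things follow, and they are two views of the same variance. Over repeated trials, the arm comparison carries noise that baseline could remove. In the one trial actually run, a chance baseline difference between arms is mis-corrected, usually over-corrected, and pushes the estimate one way.

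The choice has to be made in advance. Section 5.2 says interpretation will rest on the primary analysis defined a priori, so an adjustment added after an imbalance is seen would be only supportive. The trial is open-label with a self-reported outcome, so a visible baseline difference would invite dispute.

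**Working it through.** **Inputs from the plan.** Baseline SD 8.5; threshold 0.5 × 8.5 = 4.25; rates 40% and 60%; two-sided alpha 0.05; 80% power; 214 patients (107 per arm), inflated to 235; 1:1 allocation.

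**Assumed inputs.** The documents give neither r, the baseline-to-12-week correlation, nor k, the 12-week SD divided by the baseline SD. Both are varied: r = 0.3, 0.5, 0.7, 0.8 and k = 1, 1.2, 1.4.

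**The plan's own figure.** Two-proportion formula without correction: [1.96√(2 × 0.5 × 0.5) + 0.8416√(0.24 + 0.24)]² / 0.2² = 96.9 per arm, so 194 in total. With continuity correction: (96.9/4) × [1 + √(1 + 4/(96.9 × 0.2))]² = 106.7, so 107 per arm and 214 in total, which matches. Exact power of Fisher's test at 107 per arm is 0.795. 214 × 1.10 = 235.4, which matches 235. None of this depends on baseline adjustment.

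**Linear models of change.** In units of the baseline variance, change has variance 1 + k² − 2rk. The residual variance after fitting baseline is k²(1 − r²). The ratio is k²(1 − r²)/(1 + k² − 2rk), which at k = 1 reduces to (1 + r)/2.

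| k | r=0.3 | r=0.5 | r=0.7 | r=0.8 |
|---|---|---|---|---|
| 1 | 0.65 | 0.75 | 0.85 | 0.90 |
| 1.2 | 0.76 | 0.87 | 0.97 | 1.00 |
| 1.4 | 0.84 | 0.94 | 1.00 | 0.98 |

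The ratio never exceeds 1. It reaches 1 when the slope rk equals 1.

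**Primary logistic model.** Simulated with 4,000 replicates, 107 per arm, normal scores, 40% versus 60%, strata not simulated. Power without → with baseline:

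| k | r=0.3 | r=0.5 | r=0.7 | r=0.8 |
|---|---|---|---|---|
| 1 | 0.835→0.915 | 0.825→0.893 | 0.839→0.875 | 0.836→0.860 |
| 1.2 | 0.820→0.878 | 0.837→0.868 | 0.835→0.846 | 0.832→0.837 |
| 1.4 | 0.838→0.879 | 0.844→0.859 | 0.838→0.841 | 0.834→0.841 |

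A second version put the stratification factors in both models (2,500 replicates; assumed 8 sites, 40% chemotherapy, 40% tamoxifen, chemotherapy lowering baseline by 0.5 SD, blocks of 4 and 6):

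| k | r=0.3 | r=0.5 | r=0.7 | r=0.8 |
|---|---|---|---|---|
| 1 | 0.858→0.919 | 0.853→0.898 | 0.853→0.882 | 0.850→0.877 |
| 1.2 | 0.840→0.899 | 0.851→0.867 | 0.839→0.840 | 0.856→0.856 |
| 1.4 | 0.854→0.884 | 0.842→0.852 | 0.855→0.856 | 0.841→0.847 |

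A separate simulation at k = 1 (3,000 replicates, no strata) agrees: for example 0.845→0.922 at r = 0.3 and 0.834→0.854 at r = 0.8. With no treatment effect, rejection at k = 1 was 4.6% to 5.7% without baseline and 4.6% to 6.1% with it, across the runs.

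**Where the logistic gain comes from** (k = 1; r = 0.3, 0.5, 0.7, 0.8). The standard error of the log odds ratio rises, from 0.281 to 0.329, 0.313, 0.299, 0.293. The odds ratio moves further from 1, from about 2.27 to 2.93, 2.69, 2.50, 2.41, and the second effect outweighs the first. On the risk-difference scale the standardised estimate is more precise: its SE falls from 0.0666 to 0.0587, 0.0610, 0.0633, 0.0644, which is about 12%, 8%, 5% and 3%.

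**Chance imbalance at k = 1.** The SE of the baseline difference is 8.5 × √(2/107) = 1.16 points. A one-SE imbalance shifts the mean-change difference by (1 − r) × 1.16 = 0.81, 0.58, 0.35, 0.23 points. Dividing by the SD of change, 8.5√(2(1 − r)), and multiplying by the normal density at the 40% point (0.386) gives a rate shift of about 3.1, 2.6, 2.0 and 1.7 percentage points, against a design difference of 20.

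**The case against.** The strongest reply is that nothing here is wrong. Randomisation makes the planned comparison valid on average, every stratification factor is in the model, and the sample size does not count on baseline adjustment. The figures above use 107 per arm. With the full target, about 117 per arm, planned power is about 86% before any dilution from carrying observations forward. All of that stands, and it limits the point to a recommendation.

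The gain may also be close to nil. Patients start a drug whose side effects motivate the trial, so spread may well widen. At k = 1.2 to 1.4 with r = 0.7 to 0.8, three of the four stratified comparisons gain 0.1 point or less. This stands too. The 8-point gain belongs to the corner r = 0.3, k = 1.

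The imbalance shift is not a further harm on top of lost efficiency. At r = 0.3, √(0.0666² − 0.031²) = 0.0589, almost exactly the adjusted SE of 0.0587. The planned interval already contains that variation, so it should be read as the single-trial view of the same loss and not as bias.

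Dichotomising costs more: under the same model with k = 1, a linear analysis of continuous change has 95% to 96% power even without baseline. That is a separate matter and does not remove the case for the covariate, which takes that analysis to 97% to 99.5%.

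Finally, 5.2 does not expressly exclude other covariates, so their absence is inferred from none being named. If baseline adjustment is intended, 5.2 still has to say so.

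**Conclusion.** The concern holds, as a change that should be made and not as a flaw that invalidates the plan. The primary model and the other FACT regressions omit a prognostic covariate that is already scheduled for every patient.

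Over the range examined, adding it raises primary power by about 0 to 8 percentage points from a starting value of about 83%, and reduces linear-model variance by 0% to 35%. Apart from one degree of freedom, it does no harm in the linear models. The omission itself is certain from the text. The size rests on assumed r and k, normal scores and, for the stratified figures, an assumed mix of sites and treatments. The benefit is extra margin against a false-negative result and a primary estimate that stands up if the arms differ at baseline.

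**What to change.** In 5.2, prespecify:

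- the continuous baseline FACT-ES total as a covariate in the primary logistic model, alongside the stratification factors;
- the matching baseline total, subscale or item score in every linear or logistic model of FACT-ES or FACT-B change;
- a standardised risk difference with its 95% confidence interval beside the odds ratio, which becomes conditional on baseline. This keeps a marginal effect that corresponds to the 40% versus 60% design;
- the unadjusted t-test and chi-squared comparisons as descriptive only.

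The same paragraph should give one rule for missing baseline scores. This gap exists with or without the covariate: 5.2 includes all randomised patients, carrying forward cannot supply a missing baseline, and only the per-protocol set is limited to patients "who complete both the baseline and 12 week FACT-ES score". One option is multiple imputation from the stratification factors, age and later FACT scores, with counts by arm. The rule would need to be reconciled with the carry-forward rule for 12 weeks.

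The cost is a few sentences in 5.2 and one extra estimator. It needs no new data, visits or patients.

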2 OUTCOMES

2.1 Primary Outcome

- Endocrine toxicity and tolerability measured by the change in total FACT-ES score (a validated subscale of the FACIT measurement system) from baseline to 12 weeks following the beginning of endocrine therapy

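### Testing the continuous 12-week FACT-ES change only as a 4.25-point responder gives up about 13 points of power at 214 patients if change scores are roughly normal with equal SD

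*Combined protocol and SAP*

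**What the plan says.** Section 2.1 (Primary Outcome) sets the primary outcome as "Endocrine toxicity and tolerability measured by the change in total FACT-ES score", from baseline to 12 weeks. It defines no responder.

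Section 5.1 (Sample size) introduces one. Taking half of a baseline SD of about 8.5, it says that a clinically meaningful change "from baseline to 12 weeks would be a change of 4.25 or greater". The trial is sized on the proportion of patients reaching it, "40% with a clinically meaningful change in one arm and 60% in the other", with Fisher's exact test "using a two-sided, alpha=0.05". The result is that "we would need 214 total patients to achieve 80% statistical power", and "the target sample size will be inflated by 10% to a total of 235".

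Section 5.2 (Analysis Methods) then states: "The primary analysis will be based on a logistic regression analysis with adjustment for stratification factors". It does not name the dependent variable. Linear regression adjusted for stratum and t-tests for continuous measures are also planned, but as further analyses. The closing paragraph of 5.2, on compliance and loss to follow-up, treats everything except the primary analysis as supportive.

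**The concern.** The outcome is a numeric score, and the primary model can use only whether each patient falls above or below a cut. That the cut is 4.25 points is an inference, though a sound one, because no other binary form of the outcome appears. On that scale a change of 5 points counts the same as a change of 25, and a change of 4 counts the same as none.

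The 0.5-SD rule is cited in 5.1 as a guide to whether a change is clinically meaningful. Nothing in the documents says that the comparison between arms has to be made on that scale.

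What is at stake is efficiency. If timing does have an effect of the size the plan calls important, the cut raises the chance of a null primary result with the same patients and questionnaires. Because 5.2 gives the other analyses a supportive role, a clear result from the planned linear regression could not replace a null primary one.

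**Working it through.** **Inputs.** From 5.1: 40% v 60%, two-sided alpha 0.05, 80% power, 214 patients inflated to 235, cut 4.25 = 0.5 × 8.5. From 5.3: 1:1 allocation, so 107 per arm at 214. Added assumption, not in the documents: change scores are normal with the same SD in both arms, so that timing shifts the whole distribution.

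**1. The plan's own figure.** The two-proportion formula, with p̄ = 0.5, gives

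n = [1.96·√(2 × 0.5 × 0.5) + 0.8416·√(0.4 × 0.6 + 0.6 × 0.4)]² / 0.2² = 96.9 per arm.

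The continuity correction gives (96.9/4)·[1 + √(1 + 4/(96.9 × 0.2))]² = 106.7, rounded up to 107 per arm, or **214**. The stated figure reproduces. Inflation: 214 × 1.10 = 235.4, stated as 235.

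**2. Power on the cut scale.** These are exact enumerations over two binomials, 0.40 v 0.60. The unadjusted Wald test of the log odds ratio stands in for the logistic regression.

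| N | Fisher | Chi-squared | Wald (logistic) |
|---|---|---|---|
| 214 (107 + 107) | 79.5% | 83.2% | 83.2% |
| 235 (117 + 118) | 84.8% | 87.1% | 87.1% |

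Because counts are discrete, the value near 235 depends on the exact split: 117 + 117 gives 88.2% by chi-squared. A fair statement is about 87 to 88%.

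**3. Power on the full scale.** The shift that moves the proportion above one cut from 40% to 60% is

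d = z(0.6) − z(0.4) = 0.2533 + 0.2533 = 0.507 SD.

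The noncentrality at 107 per arm is 0.507/√(2/107) = 3.71, so t-test power is 95.8%. At 117 + 118 it is 97.2%.

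**4. Loss for the planned logistic model.**

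- At 214: 95.8 − 83.2 = 12.6 points, about 13.
- At 235: 97.2 − 87.1 = 10.1 points; with about 88% on the cut scale, about 9.

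Simulated models adjusted for tamoxifen and chemotherapy agree: 82.7% (logistic) v 95.2% (linear) at 214, and 86.9% v 97.3% at 235.

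Put another way, the full-scale analysis reaches 80% power with 63 per arm (126 in all). At 214 it has 80% power for a shift of 0.385 SD. With the cut midway between the arm means, that is a responder difference of 2Φ(0.385/2) − 1 = 15.3 points.

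**5. Dependence on shape.** Simulated power at 107 per arm, with 40% v 60% held fixed. The cut analysis has about 83% throughout.

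| Shape of change scores | t-test | Rank test on full score |
|---|---|---|
| Normal | 96% | 95% |
| Logistic | 91% | 92% |
| Skewed (gamma, shape 2) | 91% | 98% |
| t, 5 df | 86% | 92% |
| t, 3 df | 69% | 89% |
| Laplace (sharply peaked) | 64% | 79% |

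A mixture of 70% of patients at SD 1 and 30% at SD 2.5 gives a t-test power of about 80%, slightly below the cut. The advantage of the t-test therefore runs from about 13 points to a reversal. The rank test beats the cut in every shape in the table except Laplace.

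**The case against.** **The responder is the plan's clinical target.** Section 5.1 defines importance as a 20-point difference in responder rates, the trial is sized for that, and the economic evaluation in 5.2 needs a binary toxicity case. A mean difference answers a different question. This stands as a reason to keep the responder analysis prominent. It does not require the responder to be the primary test, since 2.1 states the outcome as a change in score.

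**The trial has enough power.** This also stands. A reader might infer that the trial is underpowered or that its sample size is wrong. The documents do not support that: 214 reproduces, the logistic analysis has about 83% power there, and even Fisher's test has 79.5%.

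**The loss could be put higher.** A reader might quote 16 points (95.8 − 79.5). That compares against Fisher's test, which the plan uses only for sizing. For the logistic regression named in 5.2 the figure is about 13 at 214 and 9 to 10 at 235.

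**40% v 60% does not fix the loss.** This stands. Section 5.1 gives a baseline SD only, with no SD or shape for the change. Many patients with little change and a few with large change is a plausible pattern for symptom scores, and a bounded score does not rule it out. This is why the fix includes a rank-based check.

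**The continuous change is analysed anyway.** It is, as a secondary outcome (2.2) and by linear regression (5.2). That makes the change cheap, but leaves the primary test on the cut scale.

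**4.25 as a margin between arms.** A reader might want to judge the mean difference against 4.25 points. Section 5.1 defines 4.25 as a patient's change from baseline, so it does not supply that threshold. The implied shift would be 0.507 × 8.5 = 4.3 points if the SD of change were 8.5, but that closeness gives 4.25 no such role.

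**Conclusion.** The point holds as an avoidable loss of efficiency. It rests on the inference that the logistic outcome is the 4.25-point responder, and its size rests on an unstated normal, equal-SD shift equivalent to 40% v 60%. On those terms the chance of missing the effect at 214 patients is about 17% on the cut scale and about 4% on the full scale; at 235 it is about 12 to 13% and 3%.

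Other shapes of change score can shrink the gain or turn it into a loss for a t-test, so the benefit is likely but not guaranteed. The change is worth making before the data are analysed, but the plan's power statement is not wrong without it. A null primary result also could not be put down to the cut on this evidence alone.

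**What to change.** **In 5.2:**

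- Make the primary analysis a linear regression of the 12-week change in total FACT-ES on arm and the stratification factors, reported as an adjusted mean difference with 95% CI.
- Add a rank-based analysis of the full score as a sensitivity check.
- Keep the logistic regression of the 4.25-point responder as the first supportive analysis, with proportions by arm. State there that 4.25 is the cut and which direction of change counts, since neither is stated now.
- Do not use 4.25 as a threshold for the difference between arms.

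**In 5.1:** keep 214 and 235. Add that 214 gives about 96% power for the mean-difference analysis under a normal, equal-SD shift equivalent to 40% v 60%.

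**Cost:** a few sentences, with no extra patients, visits or data. The headline result becomes a mean difference, which some readers find harder to interpret, and the responder proportions become supportive.
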